**Figure 1. Assessment and Initial Management of Tumor Lysis Syndrome (TLS)**

#### **5.4.6.9. Management of Avelumab Immune-Related Adverse Events**

Since inhibition of PD-L1 stimulates the immune system, irAEs may occur. Treatment of irAEs is mainly dependent upon severity as reported in Table 6:

- Grade 1 to 2: treat symptomatically or with moderate-dose steroids, more frequent monitoring;
- Grade 1 to 2 (persistent): manage similar to Grade 3 to 4 AE;
- Grade 3 to 4: treat with high-dose corticosteroids.

For any irAE of any grade, the investigator may consider consulting with the sponsor's medical monitor if deemed necessary.

Treatment of irAEs should follow guidelines set forth in Table 6.

Some potential immune-related adverse events described with anti-PD-L1 monoclonal antibodies such as avelumab may overlap with axitinib toxicities (eg, diarrhea, liver function tests increase). Any adverse event suspected to be immune-related should be managed according to the guidance for management of immune-related adverse events in this [Section 5.4.6.9](#).

For overlapping potential immune-related toxicities Grade 2, hold both drugs used in the combination (avelumab and axitinib) and follow the specific management recommendations described in Table 6. When the event resolves to Grade  $\leq 1$ , restart therapy with axitinib. If the Grade  $\geq 2$  event does not recur, restart avelumab at the next treatment dose. If the Grade  $\geq 2$  event does not resolve to Grade  $\leq 1$  after holding avelumab for 2 treatment doses (up to 28 days) or if the Grade  $\geq 2$  event recurs after re-introduction of avelumab, permanently discontinue avelumab therapy.

For Grade  $\geq 3$  overlapping potential immune-related toxicities follow the specific guidance on Table 6 for avelumab and hold axitinib. When event resolved to Grade  $\leq 1$ , restart therapy with axitinib at reduced dose level. Avelumab should be permanently discontinued.

Table 6. Management of Avelumab Immune-Related Adverse Events		
Gastrointestinal irAEs		
Severity of Diarrhea/Colitis (NCI-CTCAE v4)	Initial Management	Follow-up Management
Grade 1 Diarrhea: <4 stools/day over Baseline Colitis: asymptomatic	Continue avelumab therapy Symptomatic treatment (eg, loperamide).	Close monitoring for worsening symptoms. Educate subject to report worsening immediately. If worsens: Treat as Grade 2, 3 or 4.

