Grade 2 Diarrhea: 4 to 6 stools per day over Baseline; IV fluids indicated <24 hours; not interfering with ADL Colitis: abdominal pain; blood in stool	Withhold avelumab therapy. Symptomatic treatment.	If improves to Grade ≤1: Resume avelumab therapy. If persists >5-7 days or recurs: Treat as Grade 3 or 4.
Grade 3 to 4 Diarrhea (Grade 3): ≥7 stools per day over Baseline; incontinence; IV fluids ≥24 h; interfering with ADL Colitis (Grade 3): severe abdominal pain, medical intervention indicated, peritoneal signs Grade 4: life-threatening, perforation	Withhold avelumab for Grade 3. Permanently discontinue avelumab for Grade 4 or recurrent Grade 3. 1.0 to 2.0 mg/kg/day prednisone or equivalent. Add prophylactic antibiotics for opportunistic infections. Consider lower endoscopy.	If improves: Continue steroids until Grade ≤1, then taper over at least 1 month; resume avelumab therapy following steroids taper (for initial Grade 3). If worsens, persists >3 to 5 days, or recurs after improvement: Add infliximab 5mg/kg (if no contraindication). Note: infliximab should not be used in cases of perforation or sepsis.
Dermatological irAEs		
Grade of Rash (NCI-CTCAE v4)	Initial Management	Follow-up Management
Grade 1 to 2 Covering ≤30% body surface area	Continue avelumab therapy Symptomatic therapy (for example, antihistamines, topical steroids).	If persists >1 to 2 weeks or recurs: Withhold avelumab therapy. Consider skin biopsy. Consider 0.5-1.0 mg/kg/day prednisone or equivalent. Once improving, taper steroids over at least 1 month, consider prophylactic antibiotics for opportunistic infections, and resume avelumab therapy following steroids taper. If worsens: Treat as Grade 3 to 4.

Table 6. Management of Avelumab Immune-Related Adverse Events		
Grade 3 to 4 Grade 3: Covering >30% body surface area; Grade 4: Life threatening consequences	Withhold avelumab for Grade 3. Permanently discontinue for Grade 4 or recurrent Grade 3. Consider skin biopsy. Dermatology consult. 1.0 to 2.0 mg/kg/day prednisone or equivalent. Add prophylactic antibiotics for opportunistic infections.	If improves to Grade $\leq 1$ : Taper steroids over at least 1 month; resume avelumab therapy following steroids taper (for initial Grade 3).
Pulmonary irAEs		
Grade of Pneumonitis (NCI-CTCAE v4)	Initial Management	Follow-up Management

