Grade 1 Radiographic changes only	Consider withholding avelumab therapy. Monitor for symptoms every 2 to 3 days. Consider Pulmonary and Infectious Disease consults.	Re-assess at least every 3 weeks. If worsens: Treat as Grade 2 or Grade 3 to 4.
Grade 2 Mild to moderate new symptoms	Withhold avelumab therapy. Pulmonary and Infectious Disease consults. Monitor symptoms daily; consider hospitalization. 1.0 to 2.0 mg/kg/day prednisone or equivalent. Add prophylactic antibiotics for opportunistic infections. Consider bronchoscopy, lung biopsy.	Re-assess every 1 to 3 days. If improves: When symptoms return to Grade $\leq 1$ , taper steroids over at least 1 month, and then resume avelumab therapy following steroids taper. If not improving after 2 weeks or worsening: Treat as Grade 3 to 4.
Grade 3 to 4 Grade 3: Severe new symptoms; New/worsening hypoxia; Grade 4: Life-threatening	Permanently discontinue avelumab therapy. Hospitalize. Pulmonary and Infectious Disease consults. 1.0 to 2.0 mg/kg/day prednisone or equivalent. Add prophylactic antibiotics for opportunistic infections. Consider bronchoscopy, lung biopsy.	If improves to Grade $\leq 1$ : Taper steroids over at least 1 month. If not improving after 48 hours or worsening: Add additional immunosuppression (for example, infliximab, cyclophosphamide, IV immunoglobulin, or mycophenolate mofetil).

Table 6. Management of Avelumab Immune-Related Adverse Events		
Hepatic irAEs		
Grade of Liver Test Elevation (NCI-CTCAE v4)	Initial Management	Follow-up Management
Grade 1 Grade 1 AST or ALT > ULN to 3.0 x ULN and/or Total bilirubin > ULN to 1.5 x ULN	Continue avelumab therapy.	Continue liver function monitoring. If worsens: Treat as Grade 2 or 3 to 4.
Grade 2 AST or ALT >3.0 to ≤ 5 x ULN and/or total bilirubin >1.5 to ≤3 x ULN	Withhold avelumab therapy. Increase frequency of monitoring to every 3 days.	If returns to Grade ≤1: Resume routine monitoring; resume avelumab therapy. If elevation persists >5 to 7 days or worsens: Treat as Grade 3 to 4.

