Grade 3 to 4 AST or ALT >5 x ULN and/or total bilirubin >3 x ULN	Permanently discontinue avelumab therapy. Increase frequency of monitoring to every 1 to 2 days. 1.0 to 2.0 mg/kg/day prednisone or equivalent. Add prophylactic antibiotics for opportunistic infections. Consult gastroenterologist/hepatologist. Consider obtaining MRI/CT scan of liver and liver biopsy if clinically warranted.	If returns to Grade ≤1: Taper steroids over at least 1 month. If does not improve in >3 to 5 days, worsens or rebounds: Add mycophenolate mofetil 1 gram (g) twice daily. If no response within an additional 3 to 5 days, consider other immunosuppressants per local guidelines.
Renal irAEs		
Grade of Creatinine Increased (NCI-CTCAE v4)	Initial Management	Follow-up Management
Grade 1 Creatinine increased > ULN to 1.5 x ULN	Continue avelumab therapy.	Continue renal function monitoring. If worsens: Treat as Grade 2 to 3 or 4.
Grade 2 to 3 Creatinine increased >1.5 and ≤ 6 x ULN	Withhold avelumab therapy. Increase frequency of monitoring to every 3 days. 1.0 to 2.0 mg/kg/day prednisone or equivalent. Add prophylactic antibiotics for opportunistic infections. Consider renal biopsy.	If returns to Grade ≤1: Taper steroids over at least 1 month, and resume avelumab therapy following steroids taper. If worsens: Treat as Grade 4.

Table 6. Management of Avelumab Immune-Related Adverse Events		
Grade 4 Creatinine increased >6 x ULN	Permanently discontinue avelumab therapy. Monitor creatinine daily. 1.0 to 2.0 mg/kg/day prednisone or equivalent. Add prophylactic antibiotics for opportunistic infections. Consider renal biopsy. Nephrology consult.	If returns to Grade ≤1: Taper steroids over at least 1 month.
Cardiac irAEs		
Myocarditis	Initial Management	Follow-up Management

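### For a first Grade 3 diarrhoea or colitis, Protocol Section 5.4.6.9 stops avelumab for good while Table 6 resumes it, and nothing says which text governs

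*Protocol*

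**What the plan says.** Protocol Section 5.4.6.9 warns that some immune-related events "may overlap with axitinib toxicities (eg, diarrhea, liver function tests increase". It then gives two rules for such overlapping events.

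- **Grade 3 or higher.** For "overlapping potential immune-related toxicities follow the specific guidance on Table 6 for avelumab and hold axitinib". Once the event is back to Grade 1 or less, the site is to "restart therapy with axitinib at reduced dose level. Avelumab should be permanently discontinued". No exception is made for a first Grade 3 event.
- **Grade 2.** Both drugs are held and Table 6 is followed. Axitinib restarts on resolution, and if the "event does not recur, restart avelumab at the next treatment dose". Avelumab is stopped permanently only if the event is unresolved after two held doses (up to 28 days) or recurs on re-introduction.

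Table 6 has its own avelumab rules.

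- **Diarrhoea/colitis, Grade 3 to 4.** "Withhold avelumab for Grade 3. Permanently discontinue avelumab for Grade 4 or recurrent Grade 3". On improvement: "resume avelumab therapy following steroids taper (for initial Grade 3".
- **Liver tests, Grade 2.** Avelumab is withheld and resumed on return to Grade 1 or less, but: "If elevation persists >5 to 7 days or worsens: Treat as Grade 3 to 4". The Grade 3 to 4 row begins: "Permanently discontinue avelumab therapy. Increase frequency of monitoring to every 1 to 2 days".

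For avelumab, the immune-related AE row of Table 3 refers the site to both Section 5.4.6.9 and Table 6. No passage says which prevails if they differ.

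**The concern.** Section 5.4.6.9 and Table 6 are meant to be used together, and the section itself names diarrhoea as overlapping. For a first Grade 3 case, one paragraph tells the site to follow Table 6, which resumes avelumab, and then to stop avelumab permanently. Two sites that each believe they comply could therefore act in opposite ways: one re-exposes the patient and the other ends the drug.

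The stake is first of all patient safety. There is also a smaller analytic consequence. SAP Sections 3.2.1, 6.6.5 and 6.6.6 count an Arm A patient as a toxicity discontinuation when either avelumab or axitinib is stopped for an adverse event. A patient who stops avelumab for good is counted; one who pauses and resumes it is not. The same clinical event could thus be classified differently according to the text the site followed.

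**Working it through.** No sample size, power or alpha figure is involved, so the check sets the two texts side by side and asks what happens to avelumab in the end.

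| Event | Section 5.4.6.9 text | Table 6 | Result |
|---|---|---|---|
| First Grade 3 diarrhoea/colitis, resolved | stop for good | resume after taper | opposite |
| Grade 4 or recurrent Grade 3 diarrhoea/colitis | stop for good | stop for good | agree |
| First Grade 3 rash, if overlapping | stop for good | resume after taper | opposite, if in scope |
| Grade 3 to 4 liver tests | stop for good | stop for good | agree |
| Grade 2 liver tests, resolved within 5 to 7 days, no recurrence | restart | resume | agree |
| Grade 2 liver tests, resolved after day 5 to 7 but by day 28, no recurrence | restart | move to Grade 3 to 4 row: stop for good | diverge on a plain reading |
| Grade 2 liver tests, unresolved at 28 days | stop for good | stop for good | agree |
| Persistent or recurrent Grade 2 diarrhoea | stop for good after two held doses or on recurrence | treat as Grade 3 or 4: resumption or stop, depending on the reading | unclear |
| Grade 2 rash or thyroid event, if overlapping | hold both drugs | continue avelumab at first | differs, if in scope |

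The first step, withholding avelumab, is the same in both texts for Grade 2 and Grade 3 diarrhoea and for Grade 2 liver tests. They part on what follows.

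**Liver-test span.** Avelumab is given every 2 weeks (Section 5.4.1), so two held doses are 2 × 14 = 28 days, which reproduces the section's own limit. The span in which the texts diverge is 28 − 7 = 21 days to 28 − 5 = 23 days. A Grade 2 elevation that resolves on day 14 falls inside it.

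**Frequency.** The only data on the combination in the documents are from Phase 1b (Protocol Summary and Section 1.2.3): 47 patients, events of any cause. Intervals are exact (Clopper-Pearson) 95%.

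- Grade 3 diarrhoea: all cases were Grade 1 to 2, so 0/47; upper limit 1 − 0.025^(1/47) = 7.5%.
- Grade 3 rash: 1/47 = 2.1% (0.05% to 11.3%).
- ALT increased: 12.8% = 6/47, of which Grade 3 was 4.3% = 2/47. No Grade 4 ALT event is listed. Worst grade 1 or 2: 6 − 2 = 4, so at most 4/47 = 8.5% (2.4% to 20.4%) had a worst grade of 2.
- AST increased: 8.5% = 4/47, of which Grade 3 was 2.1% = 1/47. Worst grade 1 or 2: 4 − 1 = 3, so at most 3/47 = 6.4% (1.3% to 17.5%) had a worst grade of 2.

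The ALT and AST patients may be the same people, so the counts are not added. The Grade 2 share and the durations are not given, so no Arm A count is projected. Section 1.2.2.2 lists diarrhoea among the most frequent events of Grade 3 or higher with single-agent axitinib, but without a rate.

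**The case against.** The strongest objection concerns the liver tests. A reader might infer that each of the two named toxicities carries a firm contradiction and that a site cannot obey both texts in either case. The documents do not support that for liver tests. The Grade 2 paragraph sends the site to Table 6, and a general bullet in the same section says persistent Grade 1 to 2 events are managed like Grade 3 to 4. The texts can therefore be read in sequence: an elevation past 5 to 7 days leaves the Grade 2 route, and 28 days is an outer limit for other overlapping events. Alternatively, Table 6's instruction to treat as Grade 3 to 4 could mean medical treatment only, leaving the avelumab rule to the section. This objection stands in part. Either reading removes the contradiction, but they end in opposite outcomes, and the sequential one leaves the 28-day rule with nothing to do for liver tests. The case is unresolved, not impossible to follow.

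Three further points have weight.

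- These rules sit under a heading of recommended modifications, and the medical monitor can be consulted. Consultation is optional, however, and no default is stated.
- The protocol carries a schedule for the period after the IA3 cut-off of 28 April 2020, and Section 9.6 places interim analyses after all patients are randomized. Enrolment is therefore complete, and a correction reaches only patients still on avelumab. Section 5.4.6.5 says immune-related events may appear at any time after the first dose, so the benefit is reduced but not nil.
- The documents say more about overlap than the two examples. The Phase 1b text notes that rash, diarrhoea and raised liver enzymes are also reported with axitinib alone, and that hypo- and hyperthyroidism are expected with both drugs. That is useful context, but it does not define which events the overlap rules cover.

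None of this removes the Grade 3 diarrhoea conflict. Treating the section as the more specific rule would settle it, but the section does not claim that status and points back to Table 6 in the same paragraph. Treating Table 6 as governing would leave the section's permanent-stop sentence without effect for a first Grade 3 diarrhoea.

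**Conclusion.** The contradiction for a first Grade 3 diarrhoea or colitis is established with high confidence. Both instructions are in the current text, they concern an event the section itself names, and they lead to opposite outcomes with no stated precedence. Grade 3 rash follows the same pattern if it counts as overlapping.

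The Grade 2 liver-test case, for elevations resolving after day 5 to 7 and by day 28, is an unresolved ambiguity. Persistent or recurrent Grade 2 diarrhoea and the scope of overlapping events are wording clarifications only.

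This should be fixed, but it is not critical to the trial's conclusions. A reader might infer damage to the efficacy analyses. The documents give no basis for that: the endpoints touched are the secondary, descriptive toxicity-discontinuation summaries, and no effect on the primary PFS or OS tests is claimed. Frequency is low and uncertain on 47 Phase 1b patients. The case for acting rests on opposite re-exposure instructions for patients still on avelumab, not on an expected number of cases.

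**What to change.** By clarification letter or protocol amendment:

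- reconcile Section 5.4.6.9 and Table 6 so that both give the same avelumab action for a first Grade 3 diarrhoea/colitis, and for persistent or recurrent Grade 2 diarrhoea and liver tests;
- list which events count as overlapping, stating whether rash and thyroid events are included;
- state which passage governs if the two differ.

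Which clinical rule to adopt is for the sponsor's clinical team; this review takes no position on it. The cost is protocol text and its distribution to sites, with no new procedures or data collection.

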### 5.5. Investigational Product Storage

The investigator, or an approved representative (eg, pharmacist), will ensure that all investigational products are stored in a secured area with controlled access under required storage conditions and in accordance with applicable regulatory requirements.

Investigational product should be stored in its original container and in accordance with the label. See the dosage and administration instructions (DAI), package insert, or equivalent for storage conditions of the products and once reconstituted and/or diluted (for avelumab only).

- Avelumab must be stored in the refrigerator (between 2-8°C) or as specified in the product label.
- Axitinib must be stored at controlled room temperature (between 15-30°C) or as specified in the product label.

- Sunitinib must be stored at controlled room temperature (between 15-30°C) or as specified in the product label.

Storage conditions stated in the SRSD (ie, IB) will be superseded by the storage conditions stated on the label.

Site systems must be capable of measuring and documenting (for example, via a log), at a minimum, daily minimum and maximum temperatures for all site storage locations (as applicable, including frozen, refrigerated and/or room temperature products). This should be captured from the time of investigational product receipt throughout the study. Even for continuous monitoring systems, a log or site procedure that ensures active daily evaluation for excursions should be available. The operation of the temperature monitoring device and storage unit (for example, refrigerator), as applicable, should be regularly inspected to ensure it is maintained in working order.

Any excursions from the product label storage conditions should be reported upon discovery. The site should actively pursue options for returning the product to the storage conditions as described in the labeling, as soon as possible. Deviations from the storage requirements, including any actions taken, must be documented and reported to the sponsor.

Once an excursion is identified, the investigational product must be quarantined and not used until the sponsor provides documentation of permission to use the investigational product. It will not be considered a protocol deviation if the sponsor approves the use of the investigational product after the temperature excursion. Use of the investigational product prior to sponsor approval will be considered a protocol deviation.

Specific details regarding information the site should report for each excursion will be provided to the site.

Receipt of materials, door opening and closing, and other routine handling operations where the product(s) are briefly out of the temperature range described in the labeling are not considered excursions.

Site staff will instruct patients on the proper storage requirements for take-home investigational products.

## **5.6. Investigational Product Accountability**

The investigative site must maintain adequate records documenting the receipt, use, loss, or other disposition of the investigational product supplies. All bottles of study drug must be returned to the investigator by the patient at the end of each cycle and at the end of the trial, the sponsor will provide instructions as to disposition of any unused investigational product if the investigative site is unable to destroy at site per local procedures.

## **5.7. Destruction of Investigational Product Supplies**

The sponsor or designee will provide guidance on the destruction of unused investigational product (eg, at the site). If destruction is authorized to take place at the study site, the investigator must ensure that the materials are destroyed in compliance with applicable environmental regulations, institutional policy, and any special instructions provided by Pfizer, and all destruction must be adequately documented.

## **5.8. Concomitant Treatments**

Medications or vaccinations specifically prohibited in the Exclusion Criteria are also not allowed during the active treatment period, except for administration of the inactivated vaccines (for example, inactivated influenza vaccine).

If there is a clinical indication for one of these or other medications or vaccinations specifically prohibited during the trial, discontinuation from study therapy or medication/vaccination may be required. The final decision on any supportive therapy or vaccination rests with the investigator and/or the patient's primary physician. However, the decision to continue the patient on study therapy or medication/vaccination schedule requires the mutual agreement of the investigator, the sponsor, and the patient.

Concomitant treatment considered necessary for the patient's well being may be given at the discretion of the treating physician.

All concomitant treatments, blood products, as well as non-drug interventions received by patients from screening until the end of study visit will be recorded on the CRF.

Concomitant medications and treatments, including herbal supplements, will be recorded from 28 days prior to the start of study treatment and up to 90 days after the last dose of study treatment. All concomitant medications should be recorded in the CRF including supportive care drugs (eg, antiemetic treatment and prophylaxis), and the drugs used to treat adverse events or chronic diseases, and non-drug supportive interventions (eg, transfusions).

Concurrent anticancer therapy with agents other than avelumab and axitinib in Arm A or sunitinib in Arm B is not allowed. Medications intended solely for supportive care (ie, antiemetics, analgesics, megestrol acetate for anorexia) are allowed.

Recommended medications to treat infusion-related reactions, hypersensitivity reactions, flu-like symptoms, tumor lysis syndrome and immune-related events are reported in [Sections 5.4.6.5](#), [Section 5.4.6.6](#), [Section 5.4.6.7](#), [Section 5.4.6.8](#), and [Section 5.4.6.9](#), respectively.

### **5.8.1. Inhibitors and Inducers of CYP Enzymes**

In vitro studies with human liver microsomes and recombinant CYP enzymes indicate that axitinib metabolism is primarily mediated by the CYP3A4/5, and to a lesser extent by CYP1A2, CYP2C19, and UGT1A1.

Sunitinib is primarily metabolized by liver enzymes, in particular CYP3A4. There was a mean 1.8-fold increase in exposure of sunitinib when co-administered with ketoconazole, a potent inhibitor of CYP3A4 and a mean 4-fold decreased in exposure of sunitinib when co-administered with rifampin, a potent inducer of CYP3A4.

The concomitant use of strong CYP3A4/5 inhibitors (eg, ketoconazole, itraconazole, clarithromycin, atazanavir, indinavir, nefazodone, nelfinavir, ritonavir, saquinavir, diltiazem, telithromycin, and voriconazole) should be avoided. Selection of an alternate concomitant medication with no or minimal CYP3A4/5 inhibition potential is recommended. Although axitinib and sunitinib dose adjustments have not been studied in patients receiving strong CYP3A4/5 inhibitors, consider a dose reduction if axitinib or sunitinib must be dosed with a CYP3A4/5 inhibitor.

If coadministration of the strong CYP3A4/5 inhibitor is discontinued, the axitinib or sunitinib dose should be re-escalated (after 10 days) to that used prior to initiation of the strong CYP3A4/5 inhibitor.

Coadministration of axitinib or sunitinib with strong CYP3A4/5 inducers (eg, rifampin, dexamethasone, phenytoin, carbamazepine, rifabutin, rifapentin, phenobarbital, and St. John's wort) should be avoided. Selection of concomitant medication with no or minimal CYP3A4/5 induction potential is recommended. Moderate CYP3A4/5 inducers (eg, bosentan, efavirenz, etravirine, modafinil, and nafcillin) may also reduce the plasma exposure of axitinib or sunitinib and should be avoided if possible. Consider a dose increase if axitinib or sunitinib must be dosed with a CYP3A4/5 inducer.

If coadministration of the strong CYP3A4/5 inducer is discontinued, the axitinib or sunitinib dose should be de-escalated (after 10 days) to that used prior to initiation of the strong CYP3A4/5 inducer.

A listing of CYP3A4 inhibitors and inducers will be provided to the sites and updated as needed.

